#### 6.3.2 Experiment B (Measuring the effects of meditation on the human organism)

Subject selection: Pre-event, registered participants [name] event will be contacted (i.e. email) and made aware of the research opportunity. Registered participants who are interested will be able to follow a link to a pre-screening questionnaire. Members of [name] meditation community who pass pre-screening qualify to participate. Depending on the event, we anticipate recruiting between 10 to 100 subjects.

Control Selection: In addition, we will identify controls by asking participants if they are traveling with family/friends who will be at the event but will not participate in the event; these may be volunteers of the event, and/or family/friends of meditators participating in the event. Controls will be age and sex matched to match subjects. We anticipate recruiting between 5 and 20 control subjects. The consenting as well as some baseline data (i.e. Medical history, demographics) collection will be performed electronically prior to the event.

Pre-event: Consenting: The consent form will be provided to the selected subjects for review prior to the event. The PI or designated research staff member will go over the consent form in person or via HIPAA compliant web meeting platform (i.e. Zoom). During this time, subjects will have ample time to have all questions and concerns addressed. We may also collect baseline

measures including physiological readouts (i.e. wearables, HRVs) and/or biological data (i.e. saliva).

Immediate Pre-event: Confirming of consent and baseline data (for those who did not use online option consenting and baseline data will be done). Vitals (i.e. height, weight, heartrate, temperature, blood pressure), physiological data (i.e. HRV, EEG, wearables), and biological data (i.e. saliva, blood) will be collected from all consented subjects and controls.

During event: Data collection during the event may include additional collection of questionnaire data, physiological data and biological data.

Immediate post-event: Vitals (i.e. height, weight, heartrate, temperature, blood pressure), physiological data (i.e. HRV, EEG, wearables), and biological data (i.e. saliva, blood) will be collected from all consented subjects and controls.

Post event: Follow-up data may be collected electronically. Time points may include 1, 3, 6, 9, 12 months post-event. If baseline data collection also included physiological and/or biological data, we may collect these follow up data at the time points above as well.

#### 6.3.3 Experiment C (Measuring the effects of meditation within the meditation community)

We will be collecting data among [name] meditation community. We will focus on gathering pilot data (ie. Questionnaires and wearable data) on long term effects of meditation on well-being and function. Duration may span from several weeks to several months. Data collection time points may include baseline, 1, 3, 6, 9, 12 months post event.

# 6.4 Electroencephalography (EEG) and Quantitative electroencephalography (QEEG)

Electroencephalography (EEG, from Greek encephalon brain, writing graphs) is a method of medical diagnostics and neurological research for measuring the summed electrical activity of the brain by recording the voltage fluctuations at the head surface. The electroencephalogram is the graphical representation of these variations in the typical waveform. The EEG is a standard method used in neurology.

Quantitative electroencephalography is a further development that allows further conclusions regarding disorders by means of IT-technical procedures of the EEG data. In essence, here the amplitudes of frequencies are measured by means of the fast Fourier transform and set in relation to each other.

The QEEG data is intended to describe the change in brain activity and arousal for each participant.

For the analysis and data collection, three different arousal states will be recorded before and after the event. State 1 records the QEEG with eyes open without meditation/audiobook, state 2 records QEEG with eyes closed but without meditation/audiobook, and state 3 records QEEG with eyes closed listening to a short pre-recorded meditation by [name] or a section of

an audiobook. All participants are instructed to sit as still and calm as possible to avoid artifacts. Participants will be filmed to allow for potential artifact tracking.

We will be utilizing two different EEG device manufacturers (details follow under 6.4.2 and 6.4.3)

#### 6.4.1 EEG and QEEG – Procedure Details

Immediate Pre-event and Immediate Post-event procedure: We will measure brainwave data and acquire six recordings per participant.

Subjects: The subjects will be listening to a pre-recorded meditation from [name]. Measurements will take place with eyes open, and eyes closed (one set as baseline before pre-recorded meditation, one set during pre-recorded meditation, and possibly one set after pre-recorded meditation).

Controls: The controls will be listening to a section of an audio book. Measurements will take place with eyes open, and eyes closed (one set as baseline before pre-recorded audio book, one set during pre-recorded audio book, and possibly one set after pre-recorded audio book).

During event: EEG recording procedure details: Prior to a meditation happening during the event, some subject's EEG may be measured. Following above outlined details, subjects will be fitted with the EEG cap. The subject will meditate, and the EEG will be recorded for the duration of the meditation.

#### 6.4.2 EEG and QEEG – NeuroField Q21 device details

To obtain the EEG, subjects will be fitted with a 19+1 channel Q21 DC coupled EEG amplifier. (Channel: 19+1 (Non-Multiplexed). References: A1/A2 (ears). Ground: Channel 20. Input Range: +/- 100mV EEG, +/-5 VDC. Input noise: 0.25 V P-P, 0.1-10.0Hz. Gain: 50. Common Mode Rejection Ratio: >120dB from 0-60Hz. Single Pole Low Pass Filter: ~80Hz. Resolution: 24 bits. Sample Rate/Data Rate: +/-2.25 V. EEG Resolution: 0.02 Volts/LSB. EEG Channels Bandwidth: Software Controllable. DC Offset Measurement: Average DC Level. Sensor Contact Quality: Monitoring Via Offset Voltage. PC Connection: USB – CAN Optically Isolated. Software Compatibility: NeuroField64 & Neuroguide)

The Q21 is fast, quiet and accurate. When used with NeuroField EEG the amplifier can measure data from 0-128 Hz in real time. This amplifier acquires EEG in 21 analog to digital pipes (each channel has its own dedicated analog to digital conversion, thus avoiding the slew found in amplifiers using multi-duplex switching.) We may also collect event related potentials using NeuroField ERP which is a visual and auditory GO NOGO matching task, used to determine reaction time and processing speed, before and after the event.

#### 6.4.3 EEG and QEEG – BrainMaster device details

To obtain the EEG, subjects will be fitted with a 19 channel cap (COMBY EEG CAP, Pamel, hr) according to the International 10/20 System with linked ear montage (Fp1, Fp2, F7, F3, Fz,

F4, F8, T3, C3, Cz, C4, T4, T5, P3, Pz, P4, T6, O1, and O2). COMBY EEG Caps are manufactured with gold plated electrodes and electrodes made from sintered silver chloride (Ag/AgCl), which are currently most suited for brain bio potential detection. They have low impedance and auto-potential. Their quality is reflected in excellent selectivity and stability. The EEG recordings will be recorded using BrainAvatar 4.6.4 software (BrainMaster Technologies, Inc, Bedford, OH). BrainAvatar incorporates technology including BrainMaster's Discovery hardware devices, extensive signal processing and graphics software, and an exclusive high-speed sLORETA (standardized low-resolution electromagnetic brain tomography) voxel processor and 3D image projector. BrainAvatar is a full-featured clinically useful system, registered with the US FDA (https://www.brainmaster.com/kb-entry/?id=559) for professional clinical use, clinical EEG device, for neurological use and with a CE mark in Europe as a medically qualified biofeedback, monitoring, and imaging system.

The EEG signals are then imported into the NeuroGuide v2.9.1 software (Applied Neuroscience, Inc., Largo, FL) for computation and analysis. Data will be visually inspected and artifacts (i.e., activity collected from the EEG not produced by the brain) removed. The EEG will be processed with linked ear montage and compared with the NeuroGuide normative database, and Z-scores will be obtained. For analysis, particular attention will be given to alpha and theta amplitudes. Specifically, increased frontal theta and low alpha, increased gamma and increased alpha and theta coherence are scientific correlates for meditative states and of interest.

NeuroGuide software (Applied Neuroscience ) is an FDA Registered Database of Normative qEEG Values (510(K) Number K041263). It is a computer program that can compare the qEEG values of a given patient to the normative database and comparative produce brain maps.

Data will be averaged for the analysis across the recording epochs for each electrode (LE montage - Fp1, Fp2, F7, F3, Fz, F4, F8, T3, C3, Cz, C4, T4, T5, P3, Pz, P4, T6, O1, and O2) to get the results of the absolute power (percentage of total power), power ratios (Ratio of the difference Frequency bands) and coherence (functional connectivity in human cortex, measuring between each electrodes).

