#### Experiment B:

Immediate Pre-event and Immediate Post-event procedure:

This 3-step HRV assessment protocol will be performed on subjects:

1. Resting HRV assessment (5 minutes): Reflective of baseline HRV and cardiac coherence status

Participant instructions: Please sit quietly for the next 5-minutes without talking, try to remain as still as possible without sacrificing comfort. Do not engage in intense mental or emotional activity. To help avoid falling asleep keep your eyes open. Do not meditate or use other similar practices. Just sit quietly as if you were wanting at the bus stop for the bus. (No gum chewing, or reading magazines etc.)

2. Stress Prep (3 minutes): Reflective of ability to self-regulate and induce heart coherence on demand.

Participant instructions: During the next 3-minutes please do the following, as if you were preparing yourself mentally and emotionally for an important upcoming event or activity. Focus your attention in the center of your chest. Try and activate and experience a positive feeling such as care or appreciation for someone or some special place.

3. Deep breathing assessment (1 minute): Reflective of vagal tone capacity

Participant is guided with a visual to breathe as deeply as they comfortably can at the pace shown on the screen (5 sec in / 5 sec out i.e. resonant frequency breathing).

During event: When collecting HRV data, the participants will be instructed to apply the HRV monitor at the beginning of the day. Propper fitting will be confirmed by research study staff. For multiple day data collections, the participants will receive new electrodes as needed.

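### The EEG artifact definition leaves drowsy epochs in the eyes-closed theta readout, so unequal drowsiness between states, visits or groups can pass for a meditation effect

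*Protocol*

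**What the plan says.** Protocol section 6.4 defines three recording states before and after the event. State 1 is eyes open without a stimulus; "state 2 records QEEG with eyes closed but without meditation/audiobook"; state 3 is eyes closed while a short meditation (subjects) or audiobook section (controls) is played. Participants are asked to keep still and calm. Nothing is said about staying awake. "Participants will be filmed to allow for potential artifact tracking". The section also says the QEEG should describe arousal as well as brain activity.

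Section 6.4.3 gives the cleaning rule: visual inspection, with "artifacts (i.e., activity collected from the EEG not produced by the brain) removed". Z-scores against a normative database follow. On interpretation: "For analysis, particular attention will be given to alpha and theta amplitudes", and "increased frontal theta and low alpha, increased gamma and increased alpha and theta coherence are scientific correlates for meditative states and of interest". On aggregation: "Data will be averaged for the analysis across the recording epochs for each electrode".

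Section 6.4.2, on the other EEG device, states no artifact rule. Section 9 promises standard data cleaning in general terms.

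For the five-minute resting HRV recording in Experiment B, section 6.5.1 tells participants: "To help avoid falling asleep keep your eyes open".

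**The concern.** Sitting still with eyes closed, in state 3 while listening passively, invites drowsiness. An epoch in which the participant is dozing off contains genuine brain activity, so the artifact definition gives the person inspecting the trace no reason to remove it. That drowsiness raises theta is general EEG physiology and not a statement in the protocol. If it holds, dozing moves one of the two bands to which the analysis gives most attention in the direction listed as a correlate of meditation.

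The protocol recognises the sleep risk for HRV, but has no counterpart for the EEG recordings made with eyes closed. At stake are the state and before-after contrasts and the comparison with controls. So are the correlations of EEG with meditation experience (Aim 2) and with HRV, wearable and molecular findings (Aim 4). Each could partly reflect who was sleepier, and when.

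**Working it through.** **1. Does the rule reach drowsiness?** The definition turns on whether the activity comes from the brain. Drowsiness does, so it is outside the rule. Filming is for artifact tracking and so inherits the same definition. Sections 6.4 to 6.4.3 contain no wakefulness instruction, vigilance rating or drowsy-epoch rule.

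**2. Does it enter the outcome?** Yes. The retained epochs are averaged per electrode.

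**3. Size in one recording.** The protocol gives no EEG effect size, variance or epoch count, so there is no figure to reproduce. Let T be alert theta power, f the share of drowsy epochs and r the ratio of drowsy to alert theta (f and r assumed).

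Mean theta = T[(1 − f) + f·r] = T[1 + f(r − 1)]

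| Rise over a fully alert recording | r = 1.25 | r = 1.5 | r = 2 | r = 3 |
|---|---|---|---|---|
| f = 10% | 2.5% | 5% | 10% | 20% |
| f = 20% | 5% | 10% | 20% | 40% |
| f = 30% | 7.5% | 15% | 30% | 60% |

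**4. Size in a contrast.** For two recordings with shares f1 and f2, the bias relative to T is (f1 − f2)(r − 1).

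- Equal shares: 0 × (r − 1) = 0.
- 20-point difference, r = 1.5: 0.20 × 0.5 = 10%.
- 20-point difference, r = 2: 0.20 × 1 = 20%.

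A single recording set against the normative database has no second study recording to subtract. The table in step 3 then applies in full if the normative recordings were alert, which the protocol does not say.

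**5. Relative power.** Section 6.4.3 explains its power measure as a share of total power. If theta is 20% of the total (assumed) and the other bands do not change, a 20% rise in theta gives 24/(24 + 80) = 23.1%. That is a relative rise of about 15% instead of 20%. If alpha falls at the same time, theta's share rises further.

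**6. Effect on a test.** Assume no meditation effect, a 20-point difference in drowsy share, a standard deviation of relative change of 0.3 to 0.5 and a two-sided 5% level. Group sizes are the extremes in section 6.3.2 (10 to 100 subjects, 5 to 20 controls). With b the bias and SE = SD·√(1/n₁ + 1/n₂), or SD/√n for paired states:

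Chance of a significant result = Φ(b/SE − 1.96) + Φ(−b/SE − 1.96)

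Example, 10 vs 5, SD 0.3, b = 0.20: SE = 0.3 × √0.3 = 0.164, b/SE = 1.22, chance = 23%.

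| | b = 0.10 (r = 1.5) | b = 0.20 (r = 2) |
|---|---|---|
| 10 subjects vs 5 controls | 6.5% to 9.3% | 11% to 23% |
| 100 subjects vs 20 controls | 13% to 28% | 37% to 78% |
| State 3 vs state 2, n = 10 | 10% to 18% | 24% to 56% |
| State 3 vs state 2, n = 100 | 52% to 92% | 98% to about 100% |

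The normal approximation is rough at the smallest sizes. The direction is clear: this is bias, so a larger sample makes a false finding more likely.

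**The case against.** The strongest reply is that the design already handles this. State 2 is an eyes-closed reference, controls listen to an audiobook under the same conditions, and section 6.4.1 plans eyes-open measurements too. Section 6.4.2 allows a reaction-time task before and after the event, and the stimulus is short. This stands in part: equal drowsiness cancels. But the protocol neither ensures nor records equality, the reaction-time task is optional, and the Z-score comparison has no such counterpart. The protocol does not show that drowsiness differs either. That remains a plausible risk, for example between arrival and the end of an event.

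A second reply is that section 6.4.3 does not call its rule exhaustive, section 9 promises standard cleaning, and epoch rejection may be detailed in an SAP that is not at hand. A vigilance rule there would contradict nothing. Still, the protocol itself defines what is removed, and the generic sentence in section 9 does not widen that definition.

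Third, the low-alpha overlap is weak because alpha can drop out in drowsiness, and gamma and coherence are listed as well. This stands, and it limits the point mainly to theta. Fourth, arousal is itself of interest under section 6.4. That is a reason to keep the full analysis alongside a restricted one, but the plan offers no way to separate lower arousal from meditation.

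Finally, the work is exploratory pilot work with no confirmatory EEG test. That lowers the stakes without removing the ambiguity.

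**Conclusion.** The point holds in a limited form. As written, the cleaning rule and the averaging keep drowsy epochs in the eyes-closed theta readout, and less certainly affect low alpha. Contrasts are biased by (difference in drowsy share) × (theta ratio − 1): 20% for a 20-point difference with doubled theta, 10% at a ratio of 1.5, zero at equal shares. The shares, ratios and standard deviations are all assumptions, and the theta effect of drowsiness is general physiology. The protocol should be amended, because the EEG remains usable but a theta rise would be ambiguous without the change.

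Three stronger readings are not supported:

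- A reader might infer that the EEG cannot tell meditation from dozing at all. The other listed markers, the eyes-open state, state 2 and the controls all carry information.
- A reader might take the 5% to 60% range (shares of 10% to 30%, ratios of 1.5 to 3) as the bias in the results. It is the rise in one recording over a fully alert one; its upper end as a contrast needs 30% drowsy epochs on one side, none on the other, and tripled theta.
- A reader might see a contradiction with the HRV instruction. Eyes-closed EEG is a deliberate separate condition; the HRV text shows only that the sleep risk was recognised.

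**What to change.** Amend sections 6.4 and 6.4.3, with wording that covers both EEG devices:

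1. Instruct participants to stay awake during the eyes-closed recordings.
2. During the visual inspection already planned, flag drowsy epochs by a rule fixed in advance and applied blind to group and visit. Use signs that work with eyes closed: head drop on the existing video and slow eye movements on the frontal channels. Eye closure cannot serve, since states 2 and 3 are eyes-closed by design. Alpha drop-out alone should not serve either, since it selects on an outcome band.
3. Report the share of drowsy epochs by state, visit and group.
4. Report theta and alpha results with and without flagged epochs, and attribute a theta rise to meditation only if it persists without them. Keeping the full analysis preserves the stated interest in arousal.

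The cost is a second inspection pass on EEG and video already collected, and somewhat fewer usable epochs in the restricted analysis. No new measurement is needed.

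### EEG coherence is averaged over however many clean epochs a recording leaves; if it is formed from epoch-averaged spectra, unequal counts alone shift it

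*Protocol*

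**What the plan says.** Section 6.4.3 of the protocol sets out the EEG processing. Artifacts are handled first: "Data will be visually inspected and artifacts (i.e., activity collected from the EEG not produced by the brain) removed". Then "Data will be averaged for the analysis across the recording epochs for each electrode", and from this come absolute power, power ratios and "coherence (functional connectivity in human cortex, measuring between each electrodes". One averaging rule thus serves all three measures. The same section marks coherence as an outcome that matters: "increased gamma and increased alpha and theta coherence are scientific correlates for meditative states and of interest".

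On recording length, section 6.4.1 states "We will measure brainwave data and acquire six recordings per participant" for the sessions immediately before and after the event, which fits the three states of section 6.4 recorded twice. The third state for subjects is "eyes closed listening to a short pre-recorded meditation"; controls hear part of an audiobook. No duration is given for any state. For some subjects EEG may also be taken during the event, and there "the EEG will be recorded for the duration of the meditation". Section 6.4.3 compares the EEG with a normative database to obtain Z-scores, but describes no adjustment for how many epochs a participant contributed.

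**The concern.** Mean power is not biased by the number of epochs, so averaging over all of them does no harm there. Coherence behaves differently. When it is formed from spectra averaged over a finite number of epochs, chance alignment of phase makes it positive on average even between unrelated sites, and the excess grows as the epochs become fewer.

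A recording that loses more data to artifacts would therefore show higher coherence than a cleaner one from the same brain. The bias has the same sign at every electrode pair, so averaging over pairs does not remove it. Because the protocol looks for a rise in alpha and theta coherence, the bias falls on a measure of interest. It would mimic a rise where the meditation recording has fewer epochs than its comparator, and mask one where it has more. It would also carry into Aims 2 and 4, which relate EEG to meditation experience and to the HRV, wearable and molecular readouts.

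**Working it through.** **Inputs.** The protocol states no epoch length, epoch count, coherence value or standard deviation, so there is no figure of its own to reproduce. Assumed here: magnitude-squared coherence from independent epochs; C from 0.1 to 0.5; pairs of clean-epoch counts such as 30 v 60; 50 people (within the 10 to 100 subjects expected in section 6.3.2); SD of a person's change in coherence 0.05, range 0.03 to 0.10.

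**Step 1: the bias formula.** Expected excess ≈ (1−C)²/K. A simulation of complex Gaussian pairs, 20,000 replicates per cell, agrees with it:

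| C | K | Simulated | Formula |
|---|---|---|---|
| 0 | 30 | 0.0331 | 0.0333 |
| 0.1 | 30 | 0.0277 | 0.0270 |
| 0.1 | 60 | 0.0136 | 0.0135 |
| 0.3 | 30 | 0.0166 | 0.0163 |
| 0.3 | 60 | 0.0083 | 0.0082 |
| 0.5 | 30 | 0.0085 | 0.0083 |

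The largest gap over all cells was about 0.002, at K = 10.

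**Step 2: false difference between two recordings with the same true C.** Difference = (1−C)² × (1/K₁ − 1/K₂). For 30 v 60, 1/30 − 1/60 = 0.01667:

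- C = 0.1: 0.81 × 0.01667 = 0.0135 (0.0141 by simulation)
- C = 0.3: 0.49 × 0.01667 = 0.0082
- C = 0.5: 0.25 × 0.01667 = 0.0042

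For 50 v 60 at C = 0.1: 0.81 × (1/50 − 1/60) = 0.0027. For 15 v 60 at C = 0.1: 0.81 × 0.05 = 0.0405.

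**Step 3: effect on a paired test with no true change.** One-sample t test, two-sided 5%, n = 50, every person shifted the same way. Noncentrality = shift × √50 / SD:

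| Case | Shift | Noncentrality (SD 0.05) | False positives |
|---|---|---|---|
| 30 v 60, C = 0.1 | 0.0135 | 1.91 | 47% |
| 30 v 60, C = 0.3 | 0.0082 | 1.16 | 20% |
| 30 v 60, C = 0.5 | 0.0042 | 0.59 | 9% |
| 50 v 60, C = 0.1 | 0.0027 | 0.38 | 7% |
| 30 v 60, C = 0.1, four bins pooled | 0.81 × (1/120 − 1/240) = 0.0034 | 0.48 | 8% |

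For the first row, SD 0.03 gives 88% and SD 0.10 gives 16%. With 10 people and SD 0.05 it is 12%.

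**Step 4: the other estimator.** If coherence is computed inside each epoch (eight sub-segments in the simulation) and then averaged, the bias at C = 0.3 is 0.064 to 0.066 for 15, 30, 60 and 150 epochs. It is present but does not depend on the epoch count, so it makes no difference between recordings.

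**Step 5: equal counts.** With K₁ = K₂ the expression in step 2 is zero, so the bias cancels whenever there is no true change.

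**The case against.** The strongest objection is that section 6.4.3 does not say whether spectra are averaged before coherence is formed or coherence is formed per epoch and then averaged, and the documents do not describe how the named software computes it. Under the second method there is no differential bias. This stands, and the point is conditional on it.

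Next, epoch counts and minimum clean data are often left to an SAP, and none is shown. That keeps the point minor. It does not remove it, because the protocol states the averaging rule itself and applies it alike to a measure that tolerates unequal counts and to one that may not.

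A reader might infer that controls, being more restless, or rest runs, being shorter, will systematically show higher coherence than meditators. The documents do not support this. Section 6.4 asks all participants to sit still and films them so that artifacts can be traced. The same states are recorded before and after the event, and the audiobook section parallels the recorded meditation. No planned difference in length between groups or sessions appears. The one recording of open length is the during-event EEG, which is optional, and no comparison of it with the short recordings is specified.

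A reader might also take the 47% as the expected error rate. It needs low coherence, clean data halved in the same direction in all 50 people, and no pooling of bins. Alpha and theta are bands, so some pooling is plausible.

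**Conclusion.** The concern holds in conditional form. Section 6.4.3 lets the number of epochs behind a coherence value float, and under the natural reading of its text this shifts coherence by (1−C)² × (1/K₁ − 1/K₂) between recordings with no change in the brain. The documented sources of unequal K are artifact removal and the open-length during-event EEG.

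The size depends on assumptions that the protocol cannot settle: for 30 v 60 epochs, from about 0.004 at C = 0.5 to 0.014 at C = 0.1. The false-positive rate runs from near nominal (7–9%) when counts are close, bins are pooled or coherence is moderate, to nearly half in the least favourable case at SD 0.05. Random, unsystematic variation in K would mainly add noise. For exploratory pilot work with no stated coherence test, this is a desirable improvement and does not undermine the study. Power and power ratios are not affected.

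**What to change.** Add to section 6.4.3: coherence is computed from the same fixed number of clean epochs in every recording that is compared (all states, both sessions, subjects and controls, and the during-event EEG if it is compared with them), drawn at random or evenly spaced from those available. State a minimum below which a recording gives no coherence value, and name the estimator. Power may still use all epochs.

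The cost is a sentence or two of text, slightly less precise coherence from long recordings, and no coherence value from very short ones. With equal counts the differential bias disappears whichever estimator is used.
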